CLINICAL PATHWAYS FOR ACUTE CORONARY SYNDROMES IN CHINA

**Phase 3
Quality Care Initiation
and Evaluation
Protocol**

Chinese Society of Cardiology

THE GEORGE INSTITUTE
for International Health

Table of Contents

1. Overview	3
2. Background	4
2.1 Burden of acute coronary disease in China.....	4
2.2 The CPACS-1 study.....	4
2.3 CPACS-2.....	5
3. CPACS phase 3 Study Plan	8
3.1 Aim	8
3.2 Methods.....	8
3.3 Quality control	18
4. Statistical analysis plan	19
4.1 Effectiveness evaluation	19
4.2 Basic situation evaluation	19
4.3 QCI evaluation	20
5. Process evaluation	20
6. Economic evaluation	20
7. Time schedule	20
8. Ethics	21
9. Governance and Organization	21
Reference	23

1. Overview

Clinical Pathway for Acute Coronary Syndromes in China (CPACS) are a series of trials initiated and conducted by Chinese Society of Cardiology and The George Institute for Global Health, supported by the Ministry of Health of China, aiming at shortening the gaps between clinical practice and evidence-based medicine and improve the prognosis of patients with acute coronary syndrome (ACS) through optimizing clinical processes in diagnosis, treatment and hospitalization of ACS patients. These trials were expected to provide evidence on the improvement of hospital services' quality by the interventions with the implementation of clinical pathways for ACS as the core, as well as cost-effectiveness analysis and analysis of the barriers in implementation.

CPACS-1 was a prospective registry and follow-up study, involving 51 tertiary or secondary hospitals in 18 provinces across the country. A total of 2973 ACS patients were included. The study found that there was a big gap between Chinese hospitals and guidelines in the treatment of ACS, for example, the final diagnosis and objective examination indicators were not consistent among 20% of patients. Less than half of the ACS patients were prescribed with the four drugs recommended in the guidelines (aspirin, beta receptor blocker, angiotensin-converting enzyme inhibitor and statin drugs) when they left the hospital (Heart 2008;94:554-560; Am Heart J 2009;157: 509-516).

Between 2005 and 2010, we conducted a trial (CPACS-2) in 15,000 patients admitted to 75 hospitals (from 17 provinces) throughout China to determine whether the routine use of a quality improvement initiative, could increase evidence-based management of ACS. The trial showed that although the intervention could improve certain aspects of care (for example, the appropriate prescription of recommended therapies at discharge increased from 51.2% to 61.6% (OR 1.42; 95% CI: 1.00 to 2.02; p=0.061)), major system-level barriers including a lack of top down support, prevented universal improvement. Most patients with ACS in China present to non-tertiary hospitals in poorer areas, where the financial burden of ACS is catastrophic. However, relatively few of these hospitals were included in the CPACS-2. Furthermore the study was not powered to measure the impact of the intervention

on clinical outcomes such as in-hospital mortality. As a result, the social and economic benefits of the intervention remain unclear.

This study, Clinical Pathways for the management of Acute Coronary Syndromes – Phase 3 (CPACS-3), aims to determine the effectiveness and cost-effectiveness of a complex, quality improvement initiative in 96 non-tertiary, non-PCI hospitals throughout China in reducing the risk of major adverse cardiovascular events in patients admitted with ACS.

2. Background

2.1 Burden of acute coronary disease in China

The burden of chronic, non-communicable disease, of which cardiovascular disease comprises a significant component, has increased rapidly and substantially in China over recent years¹. Coronary heart disease now ranks first in the causes of all death as well as premature death. It is estimated that at least hundreds of thousands of people die of acute coronary events each year, and more than 10% of disability-adjusted life-year losses were caused by acute coronary events.^{2,3}

2.2 The CPACS-1 study

CPACS-1 was a prospective registry and follow-up study. From Oct 30, 2004 to May 31, 2005, CPACS-1 study recruited 2973 patients with the diagnosis of ACS from 51 tertiary and non-tertiary hospitals in 18 provinces throughout China, and followed them up at 6 months and 12 months after discharge. Two-thirds of participating hospitals were tertiary hospitals. Almost all tertiary hospitals were capable to perform percutaneous coronary intervention (PCI) and coronary artery bypass surgery. In terms of the demographic characteristics and medical history of recruited ACS patients, CPACS-1 were basically the same as those of other foreign registration studies¹²⁻¹⁵, as 63% of registered patients were men, with an average age of 65 years, 36% of whom had a history of coronary heart disease (CHD). CPACS-1 showed that the proportion of patients discharged on guideline recommended medical therapy (aspirin, β -blocker, ACEI/ARB, statin) for secondary prevention was low (Heart 2008;94:554-560; Am Heart J 2009;157:509-516) The CPACS-1 study

collected reliable information on the status of ACS patients at various levels of hospitals, revealing that there were gaps in the diagnosis and treatment of ACS patients between evidence-based medical guidelines and clinical practice in Chinese hospitals, providing important evidence for further researches.

2.3 CPACS-2

In order to narrow the gap between clinical practice and guidelines, we had designed and conducted a CPACS-2 study under the strong supports of the Disease Control Bureau and Department of Medical Administration of the Ministry of Health. CPACS-2 Study was the first cluster randomized controlled trial around the world, evaluating the effectiveness of quality of care initiatives (QCI) among ACS. The study was conducted in 75 hospitals from 17 provinces / cities across the country (50 tertiary hospitals and 25 secondary hospitals). After the pilot trial completed in 5 pre-trial centers, 70 hospitals were randomly divided into the early intervention group (A group) or the late intervention group (B group) using a stratified randomization. The initiation time of the intervention in B group was 12 month later than A group (Figure 1). In the CPACS-2 study, hospitals implementing QCI established a medical quality management team to coordinate the hospital departments and medical staff. Every half a year, data from 50 hospitalized ACS patients were continuously collected and entered into the web-based IT system. The IT system could feed medical quality management indicators back to the hospital's team in real time (Figure 2). The intervention also contained the implementation of ACS clinical pathways that includes risk stratification and different clinical pathways for unstable angina, non-STEMI and STEMI. The effectiveness of QCI intervention was evaluated by comparing the post-12-month-intervention characteristics of A group and the baseline characteristics of B group.

[figure not shown]

Figure 1. Design of CPACS-2, cluster randomized controlled trial.

[figure not shown]

Figure 2. Intervention in CPACS-2.

[figure not shown]

Figure 3. Design of CPACS-2, self-controlled trial.

The CPACS-2 study collected clinical data of 15140 ACS patients. The results showed that after comprehensive interventions, many medical quality indicators showed a trend of improvement. In randomized controlled design, comparisons of (group A, 12 months vs. baseline, group B) proportion of patients treated with guidelines

recommend four drugs (aspirin, beta-blockers, ACEI/ARB and statin) was 61.6% and 51.2% respectively (OR 1.42; 95% CI: 1.00-2.02; $p=0.061$); with the implementation of intervention, the hospital stay was significantly reduced ($p=0.001$) and the proportion of patients treated with the four drugs also significantly increased ($p=0.004$). Other indicators, such as the proportion of STEMI with reperfusion therapy, the door-to-needle time and door-to-balloon time also showed a trend of improvement, but not statistically significant. The incidence of major adverse events (including death, myocardial infarction, and stroke) in the hospital decreased, but which was only significant before controlling potential confounders ($p=0.009$).

To understand the implementation of the CPACS-2 study, obstacles to the application of clinical pathways, experience and lessons learned from this project and the impact of the medical environment on medical quality improvement measures, we conducted a process evaluation using semi-quantitative and qualitative methods. We conducted a questionnaire survey among 556 doctors, nurses and administrators from 75 hospitals participating in this study, as well as 40 in-depth interviews with doctors, nurses, administrators from 10 representative hospitals and experts from the working group to understand the problems in the implementation of QCI and the key points for future intervention. The results reflected the following issues: CPACS Phase 2 studies placed too much emphasis on scientific research rather than actions that improve quality of care; from the view of participating hospitals, there was a lack of good quality improvement (QI) teams and a lack of personnel dedicated to the work, the coordinators were overburdened, and the department leaders and the experts in this project had little time nor interest to truly participate in the implementation of this project. Besides, it was very difficult for large hospitals to change their service model, and secondary hospitals lacked the experience and infrastructure in doing academic research. The issue of medical insurance, the intense relations between doctors and patients, etc. affected the doctor's treatment decisions, and further hindered some effective treatments, such as the timely implementation of reperfusion therapy for acute myocardial infarction. Through process evaluation, we recognized that similar projects in the future should focus on one major issue (such as reperfusion treatment time), ask for more support

from the executive management, and conduct the project not only an academic research project but a quality improvement action.

3. CPACS phase 3 Study Plan

CPACS phase 3 study, as an ACS care quality improvement intervention, will be conducted in 15 provinces, including Hebei, Liaoning, Jilin, Jiangsu, Anhui, Gansu, Shandong, Shanxi, Henan, Hubei, Guangdong, Sichuan, Shaanxi, Inner Mongolia autonomous region, and Guizhou. These provinces cover all the different economic development status and geography in China and hence are having good representativeness. According to the experience and lessons learned from the CPACS-2 study, CPACS phase 3 study has adjusted its organizational structure. In order to strengthen administrative support, the CPACS phase 3 study will be led directly by the Department of Medical Administration, the Ministry of Health, and jointly implemented by the Chinese Society of Cardiology and The George Institute for Global Health. CPACS-3 study will mainly focus on county level hospitals that have limited medical resources, poorer ability of care and unable to transfer patients due to longer distance to tertiary centers. By implementing the ACS care quality improvement interventions in management of patients with ACS, the study will assist the participating hospitals to improve their technical and management capacity in ACS care. Through a rigorous controlled trial, we will evaluate the effect of the intervention, the costs and benefits, and we will conduct process evaluation.

3.1 Aim

To improve the diagnosis and treatment of patients with ACS, explore the mode of care suitable to local health resources, and maximize the application of evidence-based medicine in China's remote county-level hospitals.

3.2 Methods

3.2.1 Inclusion criteria for participating hospitals:

- (1) The time taken to transfer an ACS patient to the nearest tertiary hospital with a cardiac catheter facility is more than 90 minutes;
- (2) The hospital is highly unlikely to have the capacity to perform onsite

percutaneous coronary intervention (PCI) within the next 3 years;

(3) The director or deputy director responsible for medical care is a specialist in internal medicine and is able to set up a QCI team that is participated by directors of the internal medicine department, emergency department, and medical care management department;

(4) Already have established or are able to establish medical records for emergency patients and inpatients, as required by the project;

(5) Able to admit more than 40 ACS patients within 6 months;

3.2.2 Exclusion criteria for participating hospitals

Hospitals that participated in CPACS-2 will be excluded from CPACS-3.

3.2.3 Inclusion criteria for participating patients

Participants will be all patients who were admitted to participating hospitals (including outpatient departments and emergency department) with a final diagnosis of ACS (including those dead in hospital).

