10	Reperfusion therapy for STEMI patients	Proportion of STEMI patients who arrive hospital within 12 hours of symptom onset receiving fibrinolysis
11	Door to needle time	Proportion of AMI patients with ST-segment elevation or LBBB on the ECG closest to hospital arrival time receiving fibrinolytic therapy within 30 min from arrival to the hospital.
12	Length of stay	Mean days of hospitalization
13	Diagnosis inconsistent with examination findings	Proportion of patients with a final diagnosis inconsistent with biomarker findings

Patient satisfaction survey will focus on the experiences that the patient just went through in seeking the medical care, in order to determine the patient satisfaction level. We will ask about the reasons for patients’ dissatisfaction and the possible factors related to patient satisfaction including hygiene level of the ward, quietness

at night, communication satisfaction with nurses and doctors, timely responsive in case of problems, accessibility to the necessary information at discharge, overall satisfaction score and whether willing to recommend this hospital to others. The questionnaire will first be validated in a small group of people and to be used after proving its validity.

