3.2.7 Intervention

Each hospital will implement a quality of care improvement (QCI) initiative comprising 6 components:

- **Establishment of a quality improvement team:** The Department of Medical Administration, the Ministry of Health of China will invite each hospital to establish an ACS quality improvement team with the Director of the hospital as the designated Team Leader. The team members will include directors of departments relevant to the treatment of ACS (i.e. Emergency and General Medical) and each team will take overall responsibility for the implementation of the quality improvement initiative at their hospital.
- **Establishment of a web-based IT system for quality management (Hospital performance audit and feedback):** Standard reports on the performance of each hospital in the quality of care provided to ACS patients will be generated at 6-monthly intervals by the web-based IT system and sent to the Hospital Director, local Health Bureaus and the Ministry of Health (Figure 4). The report will provide a summary report of the pre-specified key performance indicators (KPIs) (Table 1) at each hospital based on the results for all ACS patients admitted at the end of each 6 month cycle. The report will also provide a study benchmark, against which participating hospitals can assess their own performance. After receiving the feedback reports, the QCI group should meet to discuss about the solutions to the possible problems that are identified in the reports. The group should return the suggested solutions to the CPACS-3 study team and implement those solutions immediately.

[figure not shown]

Figure 4. Web-based IT system of CPACS-3 study.

- Implementation of a clinical pathway:** Clinical pathways for the management of STEMI and NSTEMI/unstable angina will be provided to each hospital and incorporated for use as part of the patient medical record. Hospitals will be encouraged to adapt the pathway to suit the local resources (including staff) and facilities. All participating hospitals should have a meeting every 6 months to summarize the KPIs of that time period, make corresponding adjustments to the clinical pathway and feedback them to the project team.

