- Education and training for QCI teams:** The participating hospital must receive the training provided by the project team when the QCI intervention starts, which includes introduction of intervention project, feedback pathway, introduction of online training, improvement and evaluation of medical quality, patient safety, and the conception of patient-centered services. Three key members of the hospital's QCI team are required to attend.
- Web-based education for relevant staff:** Problem-based learning modules linked to professional Chinese Continuing Medical Education (CME)

programs, will be provided to clinical staff working at different levels (principally doctors and nurses) in each hospital. The education includes ACS diagnosis and treatment knowledge, and also patient safety and health care quality. Staff will be required to register to participate and complete the modules on-line. The website will record log-in details for all registered staff and a compulsory knowledge test on the website will be provided before the training started. The test also could be done at any time when after learning module started. CME points will be redeemed on passing the test (a score over 90 in 100 points totally).

- **Online access to specialist advice using the “e-consultant” program:** The e-consultant program allows hospital clinicians to access expert advice from clinical cardiologists via a web-based system. The program will have two kinds of expert advices, the first one is a web-answering system, in which doctors in the intervention group could ask questions that they face during the ACS patients’ treatment and the expert will answer them in 24 hours; the second one is the case conference system, by which the hospital under intervention will received twice case discussion with cardiovascular experts on line.
- **Patient education:** Patient-oriented educational material will be provided to all ACS patients (and their families) during their admission to hospital. The material will focus on the importance of long-term medication use and lifestyle modification.

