4.1 Effectiveness evaluation

For the primary end point (binary variable, in hospital major adverse cardiovascular events (MACE), including stroke, AMI, hospital readmission, vascular reconstruction and all-cause mortality), GLMM model will be used to evaluate the treatment effect (between intervention groups) and the time effect (between different patients in different time periods), with LOGIT/POSSION conversion of the end point. If there is neither the time effect nor the interaction term between time and intervention, the COX model or LOGISTIC regression model will be used to estimate the intervention effect after adjustment of covariates.

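### Patients enter on a final diagnosis that the intervention aims to change, and covariate adjustment is specified only for the fallback model, so a case-mix shift at crossover could bias the MACE effect either way

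*Protocol*

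**What the plan says.** **Entry.** Protocol section 3.2.3 gives the entry rule: "Participants will be all patients who were admitted to participating hospitals (including outpatient departments and emergency department) with a final diagnosis of ACS", with in-hospital deaths included. Entry thus rests on the final diagnosis, not on the complaint or findings at arrival.

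**What the intervention acts on.** The aim in section 3.1 begins "To improve the diagnosis and treatment of patients with ACS". In section 3.2.7, on the web-based training of clinical staff, the protocol states: "The education includes ACS diagnosis and treatment knowledge". KPI 13 in Table 1 (section 3.2.6) is the "Proportion of patients with a final diagnosis inconsistent with biomarker findings". Audit and feedback is an intervention component, and of the six-monthly report section 3.2.7 says: "The report will provide a summary report of the pre-specified key performance indicators (KPIs) (Table 1) at each hospital".

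**Room for change.** Section 1 reports that in CPACS-1 "the final diagnosis and objective examination indicators were not consistent among 20% of patients".

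**Analysis.** For the primary endpoint, section 4.1 says the "GLMM model will be used to evaluate the treatment effect (between intervention groups) and the time effect". Adjustment for covariates is mentioned once in that section, for a Cox or logistic model to be used if there is neither a time effect nor a time-by-intervention interaction. Section 4.2 compares patient characteristics between intervention groups, time periods and discharge diagnoses, but does not connect that comparison to the primary estimate.

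**The concern.** Randomising hospitals to wedges balances the hospitals. It does not balance the patients if membership of the analysis set is decided after the hospital's phase is known and is open to influence by the intervention. Here the denominator of the primary outcome depends on a diagnosis that the trial is trying to improve, made by clinicians who cannot be unaware of a pathway filed in the patient record. The independent data entry staff in section 3.2.5 do not change this, because they enter a diagnosis already made.

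The time effect removes case-mix trends common to all hospitals in a calendar period. It does not remove a change that occurs when a hospital crosses over, because that change coincides with the treatment term.

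The bias can go either way. If better diagnosis removes low-risk patients wrongly labelled ACS, the observed MACE rate rises under intervention and a real benefit is partly hidden. If greater alertness brings in more mild cases, the observed rate falls and can look like a benefit. The smallest effect in the power table (section 3.2.10) is a 15% relative reduction, so even a moderate shift in case mix matters.

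**Working it through.** The protocol gives no figure for a case-mix shift, so there is none to reproduce. The calculation below shows what size of bias follows from assumed shifts.

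**Inputs from the protocol**
- Baseline MACE 8.4% (section 3.2.10).
- Smallest effect in Table 3: 15% relative reduction, RR 0.85.
- CPACS-1 inconsistency 20% (section 1), used only as an upper guide to the pool that could be relabelled.

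**Assumptions not in the protocol**
- Patients who gain or lose the ACS label are low risk, with MACE m = 1% to 4%.
- The size of the shift: half of a 20% pool removed, or 10-20% extra patients added.

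**Scenario A: half of a 20% low-risk pool loses the label, no true effect**

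Rate in the other 80% = (8.4 - 0.2m)/0.8. Observed rate after halving = (0.8 × that rate + 0.1m)/0.9.

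| m | Rate in other 80% | Observed rate | Apparent RR |
|---|---|---|---|
| 1% | 8.2/0.8 = 10.25% | 8.3/0.9 = 9.22% | 9.22/8.4 = 1.098 |
| 4% | 7.6/0.8 = 9.50% | 8.0/0.9 = 8.89% | 8.89/8.4 = 1.058 |

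**Scenario A with a true RR of 0.85.** The two relative risks multiply:
- m = 1%: 0.85 × 1.098 = 0.933. Share of the reduction hidden = (0.933 - 0.85)/0.15, about 55%.
- m = 4%: 0.85 × 1.058 = 0.899. Share hidden = (0.899 - 0.85)/0.15, about 33%.

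**Scenario B: a fraction f of extra low-risk patients gains the label, no true effect**

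Apparent RR = [(8.4 + f·m)/(1 + f)]/8.4.

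| f | m = 1% | m = 4% |
|---|---|---|
| 10% | (8.5/1.1)/8.4 = 0.920 | (8.8/1.1)/8.4 = 0.952 |
| 20% | (8.6/1.2)/8.4 = 0.853 | (9.2/1.2)/8.4 = 0.913 |

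**False rejection in Scenario B.** The standard stepped-wedge variance (Hussey and Hughes; 96 hospitals, five periods, 50 patients per hospital-period, ICC 0.10, fixed period effects) gives a standard error of about 0.0061 on the risk difference. The protocol does not state alpha, so two-sided 0.05 is assumed. With d = 0.084 × (1 - RR), the rejection probability is Φ(d/0.0061 - 1.96) + Φ(-d/0.0061 - 1.96). This is about 10% at RR 0.952 and about 52% at RR 0.853, against a nominal 5%. This standard error implies less power at RR 0.85 (about 54%) than the 85% in Table 3, which is a separate matter. A smaller standard error, as Table 3 would imply, makes these false-rejection rates higher.

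**The case against.** **Section 4.1 does not exclude covariates.** It names the effects to be evaluated, which need not be a closed list of model terms, and section 4 leaves even the choice between GLMM and GEE open. A separate SAP could supply the covariates. This stands in part: a reader might infer that the protocol has decided on an unadjusted primary model, and the text does not say so. But the protocol carries its own section headed as the statistical analysis plan, and there it attaches adjustment to the fallback model and not to the primary one. That is more than silence, and it makes adjustment depend on a data-driven switch.

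**The 20% is not a count of patients without ACS.** This stands. A reader might take section 1 to mean that one patient in five was wrongly enrolled and at low risk. It says only that the final diagnosis and the objective indicators disagreed. Some of that may be relabelling between unstable angina and NSTEMI, which leaves entry unchanged. CPACS-1 hospitals were also two-thirds tertiary (section 2.2), unlike the hospitals here. The figure is at most an upper guide.

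**A gross shift would be visible.** Section 4.2 compares patient characteristics by group and period, and KPI 13 is itself a secondary outcome. This also stands in part: the comparison would help show a shift, but nothing says how the primary result would then be read, and enrolled numbers by hospital-period are not mentioned.

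**The data may not be there.** Section 3.2.5 confirms demography and clinical manifestations, and Table 1 implies the arrival ECG and biomarkers. Appendix 1 is not in the document, so history of coronary disease and haemodynamic status cannot be assumed to be collected.

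**The remedy is partial.** Agreed: covariates correct only measured case mix, and ECG or biomarker testing may itself change under the intervention (KPI 1 is door-to-ECG time).

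**Conclusion.** The point holds as a weakness that should be put right, not as a demonstrated bias. Entry is on a final diagnosis assigned after the hospital's phase has begun, the intervention works on that diagnosis, and section 4.1 as written specifies adjustment only for the fallback model. A shift at crossover would pass into the treatment estimate.

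Under the stated assumptions, halving a 20% low-risk pool gives an apparent RR of 1.10-1.06 with no true effect and hides about 33-55% of a 15% reduction. A reader who adds the two changes instead of multiplying the relative risks would reach 40-65%, which overstates it. Adding 10-20% low-risk patients gives an apparent RR of 0.95-0.85, at the extreme about the size of the smallest effect in Table 3.

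These are illustrations. The documents support neither a particular size nor a particular direction, and a small shift would do little harm.

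**What to change.** In section 4.1:

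- **(a) Primary model.** State that the primary GLMM, not only the fallback model, is adjusted for pre-specified characteristics fixed at presentation: age, sex, clinical presentation and ST elevation on the first ECG, with history of coronary disease and haemodynamic status on arrival if appendix 1 collects them. Do not adjust for final diagnosis, which the intervention can change.
- **(b) Sensitivity analysis.** Repeat the primary analysis in patients with objective ECG or biomarker evidence of ACS. State its limits: it drops some unstable angina, and the intervention may change how often and how early tests are done.

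In section 4.2:

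- **(c) Case mix.** Extend the planned comparison to the number of patients enrolled by hospital-period and phase, and say that it will be used in interpreting the primary result.

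The cost is wording in the analysis sections, with no change to design, hospitals or treatment, provided the chosen covariates are on the discharge form. Some patients will have missing covariate values, and the handling of these needs a sentence. Adjustment will reduce the bias, not eliminate it, so (b) and (c) are needed alongside (a).
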